6.4. Covariates

Log-transformed 28-day seizure rate [$\log_e(28\text{-days seizure rate}_b + 1)$] at baseline will be utilized as a covariate in the linear model used in the primary analysis, and for secondary analyses utilizing a similar model.

Additional terms considered in the primary analysis and included in the responder rate analysis are age strata and geographic region. Because it is anticipated that this study will have many investigator centers having very few subjects in each treatment group, age strata, and geographic region combination; a pre-specified pooling will take place (See [below](#)).

Two covariates about age are defined as follows.

Age strata will be defined as Stratum 1: 5-7 years of age; Stratum 2: 8-11 years of age; Stratum 3: 12-16 years of age; or Stratum 4: 17-65 years of age. This covariate is applied to primary analysis.

Age group will be defined as: group 1, 5-16 years of age (at randomization); group 2: 17-65 years of age (at randomization). This covariate is applied to the analysis of primary efficacy endpoint as a sensitivity analysis. This age group definition will also be used to investigate treatment-by-age interaction for the primary efficacy endpoint.

Age will be defined as subjects' age at randomization. If a subject turns 66 at randomization after screening, he/she will be counted in the 17-65 age group.

Region will be defined as follows (Upon closing of the randomization, region determinations will be further evaluated-See [contingency plan](#)):

- *United States (US)*: Subjects who participate in the U.S. or Puerto Rico centers will be pooled together;
- *European Union*: All subjects who participate in European Union (eg, Austria, Belgium, Denmark, France, Germany, Greece, Italy, Netherlands, Portugal, Spain, Sweden, United Kingdom, Bulgaria, Croatia, Czech Republic, Estonia, Hungary, Lithuania, Poland, Romania, and Slovakia,) centers will be pooled together. The member countries of European Union are explained in more detail at https://europa.eu/european-union/about-eu/countries_en;
- *Asia-Pacific*: All subjects participating in Asia-Pacific (China, India, Korea, Malaysia, Philippines, Singapore) centers will be pooled together;
- *Others*: All subjects not participating in above three regions (eg, Russian Federation, Ukraine, Belarus, Bosnia and Herzegovina, Serbia, Montenegro, Turkey) centers will be pooled together.

Any region not enrolling any subjects will not be included in the analysis.

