The difference in the least squares means and their standard errors for these 2 pair-wise comparisons will be used for constructing test statistics and 2-sided 95% confidence intervals. Results will be reported as “percent reduction in seizures from baseline” relative to placebo. For example, a difference between 1 of the pregabalin doses and placebo of -0.358 on the log-transformed scale for the 28-day seizure rate, translates into a 30.1% reduction in the 28-day seizure rate of the pregabalin group from the placebo group (ie, $100\% * [\exp^{-0.358} - 1] = -30.1\%$).

An additional back transformation will be calculated for percent reduction in seizures for each pregabalin treatment group relative to placebo for presentation as follows:

$$100\% \times \frac{[\exp(\text{LSMean(pregabalin)}) - 1] - [\exp(\text{LSMean(placebo)}) - 1]}{\exp(\text{LSMean(placebo)}) - 1}$$

The 28-day seizure rate of log scale in the double-blind treatment phase will be summarized by each month and the entire 12-weeks double-blind period for each treatment group, age group [pediatrics overall (<17 years) and adults (17-65 years)], and geographic region.

Contingency plan for the primary ANCOVA analysis model

If after unblinding, the primary ANCOVA analysis model as described above performs well without any issues, the primary analysis model will stay as described above. However, in case of ANCOVA analysis issues, for example, with convergence or missing cells in a particular treatment within a region or within an age strata, the cause of the analysis model issues will be mitigated, for example, as follows:

- If a small region, say US region, causes the model issue alone, the small region (say US region) will be pooled with European Union; Other ANCOVA model terms will stay as is;
- If age strata causes the model issue alone, the age group (5-16 years of age and 17-65 years of age) as described in [Section 6.4](#) will be used instead of the age strata; Other ANCOVA model terms will stay as is;

- If both a small region and age strata cause the model issue, then ANCOVA analysis will be performed with the small region (say US region) pooled with European Union and age group (instead of age strata), Other ANCOVA model terms will stay as is.

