Other analyses of continuous dependent variables with ANCOVA model will follow the same procedure as the primary efficacy endpoint analysis. Responder rates and any other binary variables that use the same planned model as primary efficacy endpoint analysis will similarly be adjusted as needed.

Sensitivity Analysis

As a sensitivity analysis of the primary endpoint, multiple imputation methods will be used to evaluate the impact of missing data (See [Appendix 4](#)).

Subjects who discontinue the study for insufficient clinical response, adverse event, or death will be imputed based on the observed placebo distribution, regardless of randomized treatment assignment. Imputation will be based on baseline $\log_e(28\text{-days seizure rate}_b + 1)$, geographical region, baseline weight (continuous), and age strata.

Subjects who discontinue the study for other reasons, or who complete the study but have a missing double blind seizure rate, will be imputed based on observed subjects in the same randomized treatment group. Imputation will be based on treatment group, baseline $\log_e(28\text{-days seizure rate}_b + 1)$, geographical region, baseline weight (continuous), and age strata.

A sensitivity analysis will be performed using the same linear model as the primary efficacy analysis except for the age covariate, which will be applied for the 2 age groups (5-16 years of age; 17-65 years of age).

An additional sensitivity analysis will be performed using the same linear model as the primary efficacy analysis with two age groups covariate as well as pooled region of US and European Union.

A ranked ANCOVA will be performed for the change from baseline to double blind phase of log-transformed (\log_e) 28-day seizure rate for all PGTC seizures, including age strata, treatment group, and region.

A Wilcoxon-Mann Whitney test will also be performed and reported for the change from baseline to double blind phase of log-transformed (\log_e) 28-day seizure rate for all PGTC seizures.

Supplemental Analysis

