Log _e 28-day PGTC seizure rate (N, LS Mean Diff/SE)	ITT	ANCOVA	Treatment, region, 2 age groups , baseline	Days missing from Seizure Diary will be subtracted from rate calculations	Sensitivity Analysis Note: age group are Age< 17 yrs and Age>= 17 yrs. Baseline is the log of 28-day PGTC rate at baseline
Log _e 28-day PGTC seizure rate (N, LS Mean Diff/SE)	ITT	ANCOVA	Treatment, pooled region, 2 age groups , baseline	Days missing from Seizure Diary will be subtracted from rate calculations	Sensitivity Analysis Note: age group are Age< 17 yrs and Age>= 17 yrs. US and European Union will be pooled in the region class. Baseline is the log of 28-day PGTC rate at baseline
Change from baseline to double blind phase of Log _e 28-day PGTC seizure rate	ITT	Rank ANCOVA	Treatment, region, age strata, region and ranked log-BL		Sensitivity Analysis (Log-Scale). Baseline is the ranked log of 28-day PGTC rate at baseline.
Change from baseline to double blind phase of Log _e 28-day PGTC seizure rate (DB Phase)	ITT	Wilcoxon-Mann Whitney Test			Sensitivity Analysis (Log-Scale)
Raw Seizure Count	ITT	GENMOD, Poisson and negative binomial distribution with log link	Treatment, and baseline		scale parameter = Pearson for the Poisson model. Baseline for this endpoint is seizure count at baseline.

- All efficacy endpoints will be presented descriptively overall, and separately as by age group of pediatrics overall (<17 years) and adults (17-65 years).

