In order to impute missing data at the singular time point, first prepare an input dataset, making sure that it will contain only the intended donor and recipient patterns. Separate the input dataset <efficacy> into two datasets: IMP, containing all placebo subjects and those subjects from the pregabalin arms that have missing LN_SZRATE [Miss=1] and

Impstat=1; and REST, containing the rest of the subjects from the pregabalin arms (those with non-missing LN_SZRATE [Miss=0] or Impstat=2).

title1 'Pattern Imputation based on reason for DC';

```
*these sets are exhaustive and mutually exclusive;
data IMP REST;
  set <efficacy>;
  if trt ne "Placebo" and (impstat = 2 or miss = 0) then output REST;
  else output IMP;
run;
```

Call PROC MI to impute missing data at the time point using dataset IMP as input.

*order of variables matters in proc mi;

```
proc mi data = IMP out = impout n impute=100 seed = 100;
  class region age_strata;
  var region age_strata ln_bszrt ln_szrate weight;
  monotone regression(ln_szrate = ln_bszrt region age_strata weight);
run;
```

Call PROC MI to impute missing data at the time point using dataset REST as input.

*impute like randomized trt for active who are 'ignorably missing';

```
proc mi data = REST out = restout n impute=100 seed = 101 ;
  class region age_strata trt ;
  var region age_strata trt ln_bszrt ln_szrate weight;
  monotone regression(ln_szrate = trt ln_bszrt region age_strata weight) ;
run;
```

Assemble back a dataset containing all subjects.

*fully imputed integrated dataset;

```
data main ;
  set impout restout ;
run ;
proc sort data = main ;
  by _imputation_ trt ;
run ;
```

*Analysis of imputed data sets;

* Confirm the ordering of the trt variable for specifying the vector. Here it is assumed Placebo, Pregabalin Level 1, and Pregabalin Level 2 ;

```
proc glm data=main;
  by _imputation_ ;
  class region age_strata trt ;
  model ln_szrate = trt region age_strata ln_bszrt;
```

```
lsmeans trt / diff=control('Placebo') tdiff pdiff cl ;
estimate 'Pregabalin Level 1 vs Placebo' trt -1 1 0 ;
estimate 'Pregabalin Level 2 vs Placebo' trt -1 0 1 ;
ods output lsmeans=lsm diffs=lsdiff estimates=estdiffs ;
run ;
quit ;
```

```
*integrated summary of results of imputed datasets;
proc mianalyze parms(classvar=full)=lsm edf=xxx;
  class trt ;
  modeleffects trt ;
run ;
proc sort data = estdiffs ;
  by parameter _imputation_ ;
run ;
proc mianalyze data=estdiffs ;
  by parameter ;
  modeleffects estimate ;

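### SAP Section 8.1 leaves the region and age coding of the primary ANCOVA open until after unblinding, on example-only triggers that do not make the model fail

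*SAP*

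**What the plan says.** Section 8.1 of the SAP defines the primary analysis as a linear model with log baseline seizure rate, four age strata, geographic region (four regions in Section 6.4) and treatment. It has no interaction terms.

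The contingency plan in the same section begins "If after unblinding, the primary ANCOVA analysis model as described above performs well without any issues", in which case the model stays. Otherwise it acts on problems, for example "with convergence or missing cells in a particular treatment within a region or within an age strata", and "the cause of the analysis model issues will be mitigated, for example, as follows". Three remedies are listed: pool a small region (the US is the example) with the European Union, replace the four age strata by two age groups, or do both. Each is tied to a cause, and the other model terms stay.

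Section 6.4 gives another moment: "Upon closing of the randomization, region determinations will be further evaluated", with a pointer to the contingency plan.

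Two sensitivity analyses in Section 8.1 use alternative codings. One is fitted "using the same linear model as the primary efficacy analysis except for the age covariate", which takes two age groups; the other is fitted "with two age groups covariate as well as pooled region of US and European Union". Section 8.5 lists them as separate rows and notes for the second that "US and European Union will be pooled in the region class".

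**The concern.** A confirmatory model should be fixed before treatment codes are known. Here the question of whether the model has an issue is answered after unblinding. To see how the model performs, one must fit it, and the primary p-values would normally then be in view. The plan sets no count below which a region or stratum is too small, gives no closed list of issues, and names nobody who decides without sight of results.

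This would matter less if the triggers were genuine failures, since a model that cannot be fitted has to be replaced. If they are not, the plan allows a model that works to be exchanged for another. At stake are the type I error of the two sequential tests and, more practically, whether a reader can trust a Dose Level 1 result near the 5% boundary.

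**Working it through.** **1. The plan's own figure.** Table 1 (Section 2.2) gives power 0.800 for Dose Level 1: 56 per group, difference 0.358, SD 0.67, two-sided 5%. The standardised difference is 0.358 / (0.67 × √(2/56)) = 0.358 / 0.1266 = 2.83. The normal approximation gives Φ(2.83 − 1.96) = 0.807, and the noncentral t with 110 df gives 0.800. The figure reproduces. With this power, a small shift in the estimate can move the Dose Level 1 test across the boundary.

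**2. Do the named triggers break the model?**
- *Convergence.* Section 8.1 names no software procedure. The only code for this model form is the analysis step in Appendix 4, "model ln_szrate = trt region age_strata ln_bszrt", run in PROC GLM. That is a closed-form least-squares fit with no iteration to converge.
- *Empty cells.* The design has 1 + 2 (treatment) + 1 (baseline) + 3 (region) + 3 (age) = 10 columns. With 5 US subjects, the US indicator is zero for the other 168 − 5 = 163, and these identify both treatment contrasts. Check: with no Dose Level 2 subject in the US and none in the 5-7 stratum, the rank is 10 of 10 (condition number 18) and the contrast SE about 0.13. With all US subjects on placebo, the rank is still 10.

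**3. How often would a trigger occur?** The amendment log (Section 1) reports 5 US subjects from a blinded count while the study was ongoing. Randomization is stratified by site and age (Section 2.1). Block size and the spread over site-by-age cells are not given, so a range is needed. Exact probability that at least one arm has no US subject, if the total stays at 5:

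| Split of the 5 over cells | Blocks of 3 | Blocks of 6 |
|---|---|---|
| 5 | 0 | 0 |
| 3+2 | 0 | 6/25 = 24% |
| 2+2+1 | 2/9 = 22% | 71/225 = 32% |
| 1+1+1+1+1 | 31/81 = 38% | 31/81 = 38% |

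For example, 2+2+1 in blocks of 3: each pair lacks exactly one arm, the two pairs lack the same arm with probability 1/3, and the single subject is not on that arm with probability 2/3, so 1/3 × 2/3 = 2/9.

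**4. What does the choice do to the test?** From the plan: 168 subjects, SD 0.67, effects −0.534 and −0.358. Assumed: European Union/Asia-Pacific/Others 60/60/43 beside 5 US subjects; age strata 12/16/22/118; 3/15/15/10 sites; US split 2+2+1; permuted blocks within site-by-age cells. Assumed effects on the log scale (US/EU/Asia-Pacific/Others; strata 1 to 4):
- moderate: 0.3/0/0.2/−0.2; 0.3/0.15/0/−0.1
- large: 1.0/0/0.2/−0.2; 0.6/0.3/0/−0.1
- very large: 1.5/0/0.3/−0.3; 0.8/0.2/−0.2/−0.1

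Type I error, Dose Level 2 against placebo, 30,000 null trials per setting (Monte Carlo SE about 0.0013 to 0.0016), blocks of 3 / blocks of 6:

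| Effects | Planned model | Remedies applied mechanically | Smaller of planned and matching p-value, only if triggered |
|---|---|---|---|
| None | .0487 / .0501 | .0486 / .0497 | .0496 / .0514 |
| Moderate | .0487 / .0490 | .0485 / .0483 | .0500 / .0511 |
| Large | .0524 / .0486 | .0533 / .0506 | .0561 / .0553 |
| Very large | .0507 / .0499 | .0527 / .0535 | .0562 / .0597 |

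The planned model was full rank in all 8 × 30,000 = 240,000 trials, although about 22% (blocks of 3) or 32% (blocks of 6) had an empty US arm.

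Under the planned effects, with 4,000 trials per setting, a named trigger occurred and the planned and matching models disagreed on Dose Level 1 significance in about 0.4 to 0.9% of trials with no region or age effects, and about 2 to 3% with large ones. For Dose Level 2 the figure was 0.1 to 0.4%.

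**The case against.** The strongest defence is that the plan is narrower than it looks. Each listed remedy answers a stated cause, and cell counts by arm are a fact of the design that does not depend on the estimated effect. Since the planned model always fits, the contingency may simply never act. This stands in part: harm requires treating an empty cell as itself an issue. The wording permits that without compelling it.

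A second defence is that the alternative codings are reported anyway. That is true of two of the three, but both use two age groups. The multiple-imputation row in Section 8.5 keeps age strata, yet it is skipped when missing data fall below 5%, and Section 8.1 extends the contingency to other ANCOVAs. The rank ANCOVA keeps region and age strata but is a different analysis. No SAP section expressly requires the planned complete-data model to be reported once it is replaced.

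Three stronger readings are tempting, and the documents do not support them:
- *Free choice of the smallest of four p-values.* This gives 5.6 to 8.0% in the same simulations, but Section 8.1 describes no such procedure, and the top of that range needs an assumed US effect of 1.5 log units.
- *Coding decides significance in 3 to 11% of trials.* That counts any disagreement among four codings, whether or not a trigger occurs.
- *The sensitivity analyses collapse into one model after pooling.* This follows only from the wording of Section 8.1, which defines them relative to the primary model. Section 8.5 lists region and pooled region as separate rows.

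Nor do Sections 6.4 and 8.1 set rival rules: 6.4 points to the contingency plan. They simply do not name the same decision point.

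**Conclusion.** The point holds as a minor one. The SAP lets the coding of a confirmatory model be changed after unblinding, on open-ended grounds, and its own examples are not failures of that model. The rank argument needs no assumption beyond all three arms being present in the remaining regions and strata.

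The sizes do rest on assumptions. Region sizes other than the US, age sizes, site numbers, block sizes and covariate effects are not in the documents, and the simulated ranges are not bounds. The 0 to 38% for an empty US arm holds only if the US total remains 5. On these terms, mechanical use leaves type I error near 5%, and selective use within the named triggers gives about 5 to 6%. The fallback codings are sound in themselves; the defect is the timing and openness of the choice.

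**What to change.** Delete the choice after unblinding for the primary ANCOVA, and do one of the following:

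1. Preferred: keep the four-region, four-strata model as the fixed primary analysis.
2. Alternatively, set any pooling from blinded total counts, with a stated minimum per region or age stratum, in a dated SAP amendment before unblinding.

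Make Sections 6.4 and 8.1 name the same decision point, after randomization closes and before unblinding. Section 5.6 already settles protocol deviations before unblinding. Report the other codings only as sensitivity analyses; if pooling is adopted, include the stated four-region, four-strata model among them. A fallback for the logistic models may stay, because sparse cells can cause separation there.

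The cost is a few lines of text while the study is still blinded, as the amendment log says it was. Keeping the stated model spends one degree of freedom on a very small region. In the simulation this cost about 0.5 points of Dose Level 1 power against full pooling when region and age had no effect (78.5% against 79.0%), and gained about 3 points with large effects (79% against 76%). Blinded pooling costs a slightly coarser adjustment.

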
Amendment 2
 
Date: 01-Mar-2019
 
Version 3.0
	
1. Add the following equation in Section 6.1, Section 8.1, and Appendix 1 for additional presentation of percent reduction of treatment difference relative to placebo:
 $100\% \times \frac{\exp(\text{LSMean(pregabalin)}) - 1 - [\exp(\text{LSMean(placebo)}) - 1]}{\exp(\text{LSMean(placebo)}) - 1}$ 
2. Amended the seizure type for evaluation from partial seizures to PGTC seizures under Section 6.1.3.4.
 
3. Removed cognitive testing of safety endpoint under Section 6.2.
 
4. Added a sensitivity analysis with age group (5-16 years of age and 17-65 years of age) as a covariate in Section 8.1.
 
5. Added a supplemental analysis with treatment-by-age group (5-16 years of age and 17-65 years of age) interaction term in the ANCOVA model in Section 8.1.
 
6. Updated geographical region definition under Section 6.4 with consideration of enrollment by country based on SSR dataset, and updated the definition to remain consistent under Section 8.1.
 
7. Moved supplemental analysis detail from Section 7 to Section 8.
 
8. Updated a sensitivity analysis of pattern mixture model of multiple imputation under Section 8.1, Section 8.5 and Appendix 4.
 
9. Updated dependent variable of ranked ANCOVA and Wilcoxon-Mann Whitney test from “log-transformed 28 day seizure rate” to “change from baseline to double blind phase of log-transformed 28
	
1. This back transformation was requested by FDA for A0081042. It is added to be consistent with A0081042.
 
2. Correction, consistent with the protocol-specified population.
 
3. Cognitive testing was not included in the study protocol.
 
4. To differentiate results in pediatric vs adult population.
 
5. Specified in the protocol.
 
6. Based on actual enrollment.
 
7. Editorial changes.
 
8. Added more details with multiple imputation.
 
9. To be consistent with A0081042 analyses and to be able to adjust the model for any baseline seizure imbalance.
 
10. The plot is not necessary as the interaction is

--	--	--

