2.1. Study Design

This study will consist of an 8-week baseline phase, a 12-week double-blind assessment phase (including a 2-week double-blind dose escalation phase and a 10-week double-blind fixed dose phase), and a 1-week double-blind taper phase. Eligible subjects will be randomly assigned to receive double-blind treatment with 1 of 2 dose levels of pregabalin or placebo. Study drug treatments are to be taken orally twice daily (BID) in equally divided doses for 12 weeks during the double-blind assessment phase and then 1 week double-blind taper. Subjects who complete the double-blind phase of this trial may be eligible for screening for a 1-year open-label pregabalin safety study.

A total sample size of 168 subjects (ie, 56 subjects per group) is needed to have been randomized, received treatment and had a baseline and post baseline efficacy assessment. Randomization will be stratified by site and subject age (Stratum 1: 5-7 years of age; Stratum 2: 8-11 years of age; Stratum 3: 12-16 years of age; Stratum 4: 17-65 years of age). Subjects in each age stratum within site will be randomized to a fixed dose of either placebo, Dose Level 1: pregabalin 5 mg/kg/day (maximum 300 mg/day) or Dose Level 2: pregabalin 10 mg/kg/day (maximum 600 mg/day) in a 1:1:1 ratio. Approximately 30% of planned enrollment (approximately 50 subjects) will be subjects <17 years of age. Every reasonable effort will be made to enroll a minimum of 12 subjects in each of the 4 age strata.

Study Design Diagram:

*Eligible subjects may be assessed for a 1-year open-label pregabalin safety study (Study A0081106) and complete end of study activities for A0081105 at Visit 10 (V10).

** Dose Level 1: 7 mg/kg/day for pediatric subjects <30 kg and 300 mg/day for subjects ≥ 17 years of age.

*** Dose Level 2: 14 mg/kg/day for pediatric subjects <30 kg and 600 mg/day for subjects ≥ 17 years of age.

Phone visits are also scheduled for Study Days 3, 10, 17, and 89 (each with a ± 3 day window).

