Based on a meta-analysis of double-blind placebo controlled adult adjunctive therapy studies (Studies 1008-009, 1008-011, and 1008-034) using the log transformed 28 day seizure rate, the expected differences from placebo (ie, the difference in the observed least squares means after adjusting out the study-to-study differences and site clustering within study effects) were -0.668 (-48.7%) and -0.448 (-36.1%) for 600 mg/day (Dose Level 2) and 300 mg/day (Dose Level 1), respectively. This study is powered on 80% of these estimated treatment differences; -0.534 (-41.4%) and -0.358 (-30.1%) for 600 mg/day (Dose Level 2) and 300 mg/day (Dose Level 1), respectively.

A meta-analysis of Studies 1008-009, 1008-011, and 1008-034 was used to estimate a pooled standard deviation of 0.73 on the log transformed 28 day seizure rate scale, with a 95% confidence interval of [0.70, 0.76]. For the purposes of this study, a smaller standard deviation of 0.67 was used to assess the power and initial sample size requirements for comparing the 2 pregabalin group to placebo. The rationale for assuming the smaller SD of 0.67 is based on the Study 1008-034 data which included all three treatment groups of interest (i.e., placebo, 300 mg/day, and 600 mg/day). This study had a point estimate for the standard deviation of 0.72 and a 95% confidence interval for the standard deviation of [0.67, 0.77].

To ensure that the sample size is reasonably sufficient using an assumed pooled standard deviation of 0.67 on the \log_e scale, in order to provide at least 80% power to detect a

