4. HYPOTHESES AND DECISION RULES

4.1. Statistical Hypotheses

There will be 2 pair-wise comparisons of interest:

- a) Dose Level 2: pregabalin 10 mg/kg/day (maximum 600 mg/day) - placebo, and*
- b) Dose Level 1: pregabalin 5 mg/kg/day (maximum 300 mg/day) - placebo.*

Each dose of pregabalin will be compared to placebo in a pair-wise manner using a sequential step-wise testing procedure to control for multiplicity of testing such that the experiment-wise type I error rate will not exceed the 5% level of significance.

1) The first step will test the null hypothesis of equal treatment effect of Dose Level 2 vs. placebo at $\alpha=0.05$ 2-sided for the primary endpoint.

$$H_{01}: \mu_{\text{PGB Dose Level 2}} - \mu_{\text{PBO}} = \mathbf{0}$$

$$H_{a1}: \mu_{\text{PGB Dose Level 2}} - \mu_{\text{PBO}} \neq \mathbf{0}$$

2) The second step will test the null hypothesis of equal treatment effect of Dose Level 1 vs. placebo at $\alpha=0.05$ 2-sided for the primary endpoint.

$$H_{02}: \mu_{\text{PGB Dose Level 1}} - \mu_{\text{PBO}} = \mathbf{0}$$

$$H_{a2}: \mu_{\text{PGB Dose Level 1}} - \mu_{\text{PBO}} \neq \mathbf{0}$$

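### The ranked ANCOVA sensitivity analysis has two covariate lists: SAP Section 8.1 omits ranked log baseline and Section 8.5 includes it

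*SAP*

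**What the plan says.** - **SAP Section 8.1, Sensitivity Analysis.** A ranked ANCOVA is planned on the change from baseline to the double-blind phase in log "28-day seizure rate for all PGTC seizures, including age strata, treatment group, and region". No baseline term is listed.
- **SAP Section 8.5, Rank ANCOVA row.** The response is the same, and the row is also labelled a sensitivity analysis. The terms are "Treatment, region, age strata, region and ranked log-BL", and a note explains: "Baseline is the ranked log of 28-day PGTC rate at baseline".
- **SAP Section 8.1, primary model.** Log baseline rate is a continuous covariate, alongside age strata, region and treatment.
- **SAP Section 1, Amendment 2, item 9.** Part of the reason for moving the ranked ANCOVA and the Wilcoxon test to a change score was "to be able to adjust the model for any baseline seizure imbalance". This is a change log, so it shows intent and does not decide the current text.
- **SAP Sections 4.1 and 4.2.** Both steps of the test sequence are at 0.05, "2-sided for the primary endpoint". The ranked ANCOVA has no part in them.

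**The concern.** A programmer working from Section 8.1 and one working from Section 8.5 would fit different models under the same name. The SAP does not say which section governs, so the choice stays open until the data are unblinded. A sensitivity analysis is persuasive only if its model was fixed beforehand.

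The two versions also differ in quality. Subjects with high baseline rates tend to fall further by regression to the mean, so change is usually negatively related to baseline. If baseline is not a covariate, that variation stays in the error term. An arm that starts higher by chance will also tend to show a larger fall, so the change score over-corrects.

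**Working it through.** **1. The two lists side by side**

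| Term | Section 8.1 | Section 8.5 |
|---|---|---|
| Treatment | yes | yes |
| Age strata | yes | yes |
| Region | yes | yes, twice |
| Ranked log baseline | no | yes |

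The repeated region term does not alter the fit. The baseline term does.

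**2. Inputs**

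From the SAP: 56 per group (Section 2.1); log-scale effects of −0.358 for Dose Level 1 and −0.534 for Dose Level 2, and SD 0.67 or 0.73 (Section 2.2); two-sided 0.05 (Section 4.1). On the planning value, Section 2.2 says "a smaller standard deviation of 0.67 was used to assess the power and initial sample size requirements".

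Assumed: the correlation ρ between baseline and on-treatment log rate (Appendix 6 defines the symbol but gives no value); equal variances at the two times; and the stated SD read as the baseline-adjusted residual SD.

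**3. The plan's own figures**

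Power = Φ(|δ| / (SD·√(2/56)) − 1.96).

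- Dose Level 1, SD 0.67: 0.358 / (0.67 × 0.1890) = 2.827, so power is Φ(0.867) = 0.807 (Table 1: 0.800).
- Dose Level 1, SD 0.73: 0.737 (0.742).
- Dose Level 2, SD 0.67: 0.988 (0.984).
- Dose Level 2, SD 0.73: 0.972 (0.970).

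Table 1 reproduces. It concerns the primary ANCOVA; the SAP states no power for the ranked ANCOVA.

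**4. Cost of dropping the covariate, unranked approximation**

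With equal variances σ², the change score has variance 2σ²(1 − ρ) and the baseline-adjusted residual has variance σ²(1 − ρ²). Their ratio is 2/(1 + ρ), so the SD is multiplied by √(2/(1 + ρ)), which is never below 1. Example: at ρ = 0.5, 0.67 × √(2/1.5) = 0.774, and Dose Level 1 power falls from 0.807 to 0.687, a loss of 12.0 points.

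| ρ | SD without baseline | Loss, Dose Level 1 | Loss, Dose Level 2 |
|---|---|---|---|
| 0.5 | 0.774 | 12.0 | 3.3 |
| 0.6 | 0.749 | 9.2 | 2.3 |
| 0.7 | 0.727 | 6.6 | 1.5 |
| 0.8 | 0.706 | 4.2 | 0.9 |
| 0.9 | 0.687 | 2.0 | 0.4 |

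**5. The ranked models themselves**

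Both were fitted to the same 6,000 simulated trials per ρ: three arms of 56, normal log rates, residual SD 0.67, equal variances, and an assumed age and region mix with no effect on outcome. Entries are power without / with ranked baseline; losses were taken before rounding.

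| ρ | Dose Level 1 | Loss | Dose Level 2 | Loss |
|---|---|---|---|---|
| 0.5 | 0.649 / 0.759 | 11.0 | 0.932 / 0.977 | 4.5 |
| 0.6 | 0.683 / 0.762 | 8.0 | 0.952 / 0.978 | 2.6 |
| 0.7 | 0.711 / 0.766 | 5.5 | 0.962 / 0.980 | 1.8 |
| 0.8 | 0.733 / 0.769 | 3.6 | 0.970 / 0.978 | 0.9 |
| 0.9 | 0.745 / 0.764 | 1.9 | 0.975 / 0.980 | 0.5 |

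**6. How far the assumptions matter**

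Let k be the ratio of baseline SD to on-treatment SD. The variance ratio becomes (1 + k² − 2ρk)/(1 − ρ²). For k from 0.7 to 1.1 and ρ from 0.5 to 0.9, the unranked Dose Level 1 loss at SD 0.67 runs from 0 to 16.5 points. It is zero when k = ρ, because the slope of outcome on baseline is then 1 and the change score already makes the full adjustment. If 0.67 is instead read as the change-score SD, the Dose Level 1 loss is 9.7 points at ρ = 0.5 and 1.9 at ρ = 0.9.

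**7. Chance imbalance**

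Suppose the arms differ by D in mean log baseline. With equal variances the correct adjustment is ρD, while the change score subtracts D. The amount left over is −(1 − ρ)D: half of the imbalance at ρ = 0.5 and a tenth at ρ = 0.9, with the sign reversed. This is on the unranked scale.

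**The case against.** The best reply is that the intended model can largely be recovered. Section 8.1 introduces its terms with a word that need not be exhaustive, while Section 8.5 names the covariate and defines it. That narrows the choice, but Section 8.1 on its own reads as a complete list and no precedence is stated.

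A second reply concerns the amendment reason. Item 9 covered the Wilcoxon test too, which takes no covariate, so the intended baseline adjustment may be the change score itself. That is a fair reading, and for this reason the log cannot settle the matter. Two features of the current text still favour Section 8.5. An ANCOVA with no continuous covariate is an ANCOVA in name only. Also, the Wilcoxon test already analyses the same change score without baseline, so the Section 8.1 model would add only age and region to it.

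Three stronger readings are tempting, and the documents do not support them:

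- A reader might infer that Section 8.1 ignores baseline. It does not: the response is a change from baseline, and only the covariate is missing.
- A reader might infer a fixed power loss of 5 to 12 points. In the unranked calculation that range appears for Dose Level 1 only with equal variances and ρ of about 0.5 to 0.75, and the documents give no ρ. For Dose Level 2 at SD 0.67 the loss is under 5 points in both tables; at SD 0.73 the unranked loss is 5.4 at ρ = 0.5 and 2.0 at ρ = 0.75.
- A reader might treat this as the main check on the normality assumption, or as a threat to the trial's conclusion. The SAP does not rank its sensitivity analyses. It also plans the Wilcoxon test and Poisson and negative binomial models with baseline count as a covariate.

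**Conclusion.** The inconsistency is real and stands in the current text: one pre-specified sensitivity analysis has two models. The baseline-adjusted version is generally the more precise and handles a chance baseline imbalance better. Assuming normal log rates, equal variances, a residual SD of 0.67 and ρ from 0.5 to 0.9, the Section 8.1 version loses about 11 down to 2 points of power for Dose Level 1 and about 4.5 down to 0.5 points for Dose Level 2. These figures illustrate the direction and rough size; they are not estimates for this trial, because ρ and the variance ratio are not given. Primary power, type I error and the decision rule do not change. The case for correction rests on the two competing models and does not need any particular power figure.

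**What to change.** In SAP Section 8.1, state that the ranked ANCOVA of the change in log 28-day PGTC rate has the terms treatment, region, age strata and ranked log baseline 28-day PGTC rate. In the Section 8.5 row, delete the second region so that both places give the same model. Do this before unblinding. The cost is one sentence and one deleted word: baseline rate is already collected, no new data are needed, and the primary analysis is untouched.
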